These at risk subjects will be identified by either elevated Alanine Aminotransferase (ALT) liver enzyme (≥ 35 U/L), positive family history of NAFLD, and/or known existence of disease. Those participants with hepatic fat content higher than 5.5% will be recruited.

Subjects diagnosed with OSA with a high hepatic fat content (greater than 5.5%) will receive the CPAP and after 4, 8 and 12 weeks intervention they will undergo additional MRIs and have liver function blood tests completed. Also, the patient will repeat an OGTT at 12 weeks of intervention. Along with the glucose testing, liver functions, lipid panel and hemoglobin A1C will be completed. All follow up testing will be billed to the research grant. We will repeat the MRI multiple times to assess the shortest timeframe to significantly reduce intra-hepatic fat content. See study design below

Study Schedule

Screening. The screening visit in the YCCI Research Unit will be scheduled and the PI or one of the members of the research team will explain the study in detail to each subject. Each potential subject and his/her parents will be given the consent to read and consider. If deciding to participate, then a medical history, physical exam, height, weight, vital signs will be performed to ensure that the individuals are healthy and it is safe for them to participate. A three day food record and stool sample will be obtained at this time. All subjects will be asked the medical history.

The physical exam will include:

- pulse rate and regularity at rest
- body composition as measured by Tanita scale
- blood pressure, supine, sitting and standing
- auscultation of the heart with specific attention to murmurs, gallops, clicks and rubs.

During the first visit the patients will undergo to the OGTT and abdominal MRI. Pubertal female subjects will be tested for pregnancy at screening and at each MRI. The subjects will be screened for metal implants and claustrophobia using the MRRC Safety Questionnaire.

Assessment of Glucose Tolerance Status

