This protocol presents minimal risks to the subjects and adverse events or other problems are not anticipated. In the unlikely event that such events occur, serious and unanticipated and related adverse events or unanticipated problems involving risks to subjects or others will be reported in writing within 48 hours to the HIC (using the appropriate HIC forms from the website) and the NIH. The investigator will apprise fellow investigators and study personnel of all adverse events that occur during the conduct of this research by e-mail or ad hoc meeting. The protocol's research monitors; the Yale Center for Clinical Investigation Research Subject Advocates (YCCI RSAs) and NIH will be informed of serious adverse events within 48 hours of the event becoming known to the principal investigator.

- d. For multi-site studies for which the Yale PI serves as the lead investigator: N/A
 - i. How will adverse events and unanticipated problems involving risks to subjects or others be reported, reviewed and managed?
 - ii. What provisions are in place for management of interim results?
 - iii. What will the multi-site process be for protocol modifications?

17. Statistical Considerations: Describe the statistical analyses that support the study design.

Statistical Considerations:

Statistical Analysis Plan

Power and Sample Size:

The hypothesis of our primary aim is that CPAP will decrease the intra hepatic fat accumulation measured with MRI between baseline after 4, 8 and 12 weeks of intervention in obese youth. A sample size of 15 produces a two-sided 95% confidence interval with a distance from the mean paired difference to the limits (i.e., precision or margin of error) that is equal to 0.55 when the estimated standard deviation of the paired differences is 1.

Statistical Methods:

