For all analyses, a two-sided p-value of 5% will be used to test for statistical significance and will be performed using SAS v9.3 (SAS Institute, Cary, NC). We will calculate descriptive statistics (i.e., mean, SD, median, interquartile range, N and percentage) for all participants at baseline 4, 8 and 12 weeks of intervention. The difference in hepatic fat content between baseline and 4, 8 and 12 weeks will be tested using one-sample Wilcoxon signed rank-test. If necessary, we will also investigate whether or not the change (e.g., decrease) could be attributed to the differences in patients' demographic and other clinical characteristics, e.g., by the means of Wilcoxon rank sum test in patients from different groups stratified by some factor (e.g., male vs. female). This, however, pertains to hypothesis generation for a larger future study.

SECTION VI: RESEARCH INVOLVING DRUGS, BIOLOGICS, PLACEBOS AND DEVICES**A. DRUGS and BIOLOGICS N/A**

1. **Identification of Drug or Biologic:** What is (are) the **name(s)** of the drug(s) or biologic(s) being used? **N/A.**

All protocols which utilize a drug or biologic **not** approved by, but regulated by, the FDA must provide the following information:

What is the Investigational New Drug (IND) **number** assigned by the FDA?

Who holds the IND?

All protocols which utilize a radiotracer not approved by, but regulated by the FDA must provide the IND number: _____

Alternatively, use of the investigational radiotracer may be under RDRC/RSC oversight: (check if appropriate) _____

For all investigational radiotracers, attach a copy of the RDRC/RSC application (for radioisotopes used in the PET Center, PET Center personnel may complete this step)

Go to <http://rsc.med.yale.edu/login.asp?url=myApps.asp>. When you have logged in, complete the application and attach a copy to this submission

Alternatively, an **exemption from IND filing requirements** may be sought for a clinical investigation of a drug product that is lawfully marketed in the United States. If there is no IND and an exemption is being sought, review the following categories and complete the category that applies (*and delete the inapplicable categories*):

Exempt Category 1

The clinical investigation of a drug product that is lawfully marketed in the United States can be exempt from IND regulations if all of the following are yes:

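### No rule is given for the shortest time to a significant fall in liver fat, and the natural reading, the first visit with p<0.05, depends on sample size as well as biology

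*Combined protocol and SAP*

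**What the plan says.** Section V, 3 (Research Plan: General Description) schedules the scans: "after 4, 8 and 12 weeks intervention they will undergo additional MRIs". It then gives the purpose of repeating them: "We will repeat the MRI multiple times to assess the shortest timeframe to significantly reduce intra-hepatic fat content".

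Section V, 17 (Statistical Considerations) puts the same three visits into the primary hypothesis, that "CPAP will decrease the intra hepatic fat accumulation measured with MRI between baseline after 4, 8 and 12 weeks of intervention in obese youth". The sample size is justified by precision: "A sample size of 15 produces a two-sided 95% confidence interval", with a margin "equal to 0.55 when the estimated standard deviation of the paired differences is 1".

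Under Statistical Methods, "The difference in hepatic fat content between baseline and 4, 8 and 12 weeks will be tested using one-sample Wilcoxon signed rank-test", and "For all analyses, a two-sided p-value of 5% will be used to test for statistical significance". The same paragraph plans descriptive statistics at baseline and each visit, and subgroup comparisons that it calls hypothesis-generating.

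The section contains no comparison of one follow-up visit with another, no time-course model, no size of reduction that would count, and no rule for turning the three test results into a timeframe.

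**The concern.** The timing aim is worded in terms of significance, and the only significance tests on offer compare each visit with baseline. Someone carrying out the plan would most naturally name the first visit with p<0.05.

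A p-value against baseline shows whether 15 children were enough to detect the change at that visit. It does not show when liver fat fell. A significant week 8 after a non-significant week 4 does not establish that the two visits differ, and the plan never examines that difference. With the same biology, a larger study would tend to report an earlier week. At stake is a statement such as a fall that takes eight weeks, which could be quoted later although the data do not support it.

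**Working it through.** **Inputs from the documents.** n=15, single arm, paired; visits at weeks 4, 8 and 12; signed-rank test of each visit against baseline; two-sided 5%; SD of paired differences set to 1.

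**Assumed, because the documents are silent.** The size and shape of the fall, normally distributed changes, and a correlation of 0.5 to 0.8 between the changes at different visits. Data are taken as complete.

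**1. The plan's own figure.** Half-width = t(0.975, 14) × SD/√n = 2.145 × 1/3.873 = 0.554. This reproduces the stated 0.55.

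**2. Power at a single visit, n=15.** Paired t / signed-rank: 51%/48% for a true fall of 0.55 SD, 82%/80% for 0.8 SD, 95%/94% for 1.0 SD. A fall equal to the plan's own margin of error is missed at a given visit about half the time.

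**3. First visit with a significant decrease.** Exact signed-rank test (n=15: W+ ≤ 25, one-sided 0.024), unadjusted, 100,000 simulated trials per row. Entries are percentages of trials, rounded.

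| Assumed true fall | n | Correlation | Week 4 | Week 8 | Week 12 | Never |
|---|---|---|---|---|---|---|
| 0.6 SD, all present from week 4 | 15 | 0.5 | 56 | 17 | 8 | 19 |
| 0.6 SD, all present from week 4 | 15 | 0.7 | 56 | 14 | 7 | 24 |
| 0.8 SD, all present from week 4 | 15 | 0.5 | 80 | 12 | 4 | 4 |
| 1.0 SD, all present from week 4 | 15 | 0.5 | 94 | 5 | 1 | 1 |
| Linear to 0.8 SD at week 12 | 15 | 0.5 | 15 | 35 | 35 | 15 |
| Linear to 0.8 SD at week 12 | 30 | 0.5 | 28 | 52 | 18 | 1 |

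At 0.6 SD a wrong (later) visit is named in 17 + 8 = 25% of trials at correlation 0.5, and in about 20% at 0.7.

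**4. Dependence on n.** For the constant 0.6 SD fall, week 4 is named in 56% at n=15 and 87% at n=30. For the linear fall to 0.8 SD, paired-t power at weeks 4/8/12 is 16/48/82% at n=15, 29/81/99% at n=30 and 75/100/100% at n=100. The likely date moves earlier while the biology stays the same.

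**5. Does error control cure it?** Take a fixed sequence, week 12, then 8, then 4. For 0.8 SD constant from week 4, week 4 is named in 60% (correlation 0.5) to 67% (correlation 0.8), against 80% unadjusted. For the linear fall the split for week 4/8/12/never is 11/31/38/20%. Control makes late or missing dates more common overall.

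**6. Direction of error.** If a 0.8 SD fall starts only at week 8, week 4 is named in about 2% of trials. The errors are mainly late or absent dates.

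**7. What between-visit contrasts could deliver.** The SD of the difference between two visit changes is √(2(1−ρ)), which is 1.00 at ρ=0.5 and 0.775 at ρ=0.7. The half-widths are 0.554 × 1.00 = 0.55 SD and 0.554 × 0.775 = 0.43 SD. In the linear scenario each step is 0.8/3 = 0.27 SD, for which a paired t test at n=15 has about 16% power (ρ=0.5) or 24% (ρ=0.7).

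**The case against.** The strongest reply is that the documents never state a first-significant-visit rule. That is correct. A reader might infer that the plan commits to an invalid rule, but the text supports only the narrower statement that none is given and that this one is the natural reading.

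The aim can also be read as asking when a fall from baseline can first be shown, which the planned tests do address. That reading is fair, but its answer then describes a study of 15 children and not how long treatment takes to work.

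Two further inferences are tempting and do not hold. One is that the week 4 and week 8 scans serve nothing but the timing aim: the primary hypothesis names those visits too. The other is that the tests are all the plan reports: visit-wise descriptive statistics are planned, and the sample size is framed as a confidence interval, so part of the remedy is already there.

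It can also be said that the contrasts will seldom settle the question at this size. Step 7 confirms it. This limits what the fix delivers, but it does not make the first-significant-visit answer any sounder.

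**Conclusion.** The point stands as a gap in the plan that is cheap to close. The timing aim is defined by significance, no rule or between-visit comparison supports it, and the natural reading ties the answer to sample size.

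The size depends on an effect that the documents do not give. With a moderate fall (0.6 SD from week 4), a later visit is named in about 20 to 25% of trials and no visit in about 19 to 24%. These are different failures and should not be merged: a trial that never reaches significance has not named a wrong week. A reader might infer that 15 children will usually misdate the effect. The documents do not support that, because a fall of 1.0 SD present from week 4 is dated correctly in about 94% of trials, and nothing in the plan excludes such a fall. For a gradual fall the visit named is governed largely by power.

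The problem remains with complete data, and a fixed test sequence does not remove it. It is therefore separate from missed scans and from multiplicity.

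**What to change.** In Section V, 3, delete *significantly* from the timing objective. In Section V, 17:

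- Report the change in hepatic fat from baseline with a 95% CI at weeks 4, 8 and 12.
- Add the paired contrasts week 8 minus week 4 and week 12 minus week 8 in the same children, each with a 95% CI.
- State that no visit will be called the shortest time merely because it is the first with p<0.05.
- Label the timing result as descriptive estimation.

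The cost is a change of wording and two contrasts on scans already planned, with no extra children or visits. The drawback is that these intervals will be wide, so the timing answer will often be inconclusive instead of a single week.

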The signal from an appropriate area of hepatic tissue will be used to calculate the fat fraction. Importantly, an excellent correlation was reported between the liver fat content measured by FAST-MRI and liver biopsy ($r^2 = 0.853$, $p<0.001$). The hepatic fat fraction will also be calculated using a three-point Dixon technique in combination with the iterative least-squares estimation method. As this method is implemented in a steady-state free precession sequence, it allows one to obtain multiple sections (typically 10-14 slices) through the liver within a single breath-hold scan of about 25-30 seconds. A scout image requiring a breath-hold of about 12 seconds will also be obtained. The hepatic iron concentration will be calculated using a T2 weighted and intermediate weighted gradient echo sequence obtained during two breath-hold sequences of about 26 seconds each. The signal from an appropriate area of hepatic tissue will be used to calculate the hepatic iron concentration. Subjects may be asked to repeat a scan if a sub-optimal image is obtained on the first attempt.

Evaluation of Dietary Intake: This will be done by a registered dietitian. Each subject will be instructed on how to keep a 3-day food diary at the time of assent/consent. The subject will return at baseline with their food recall and will also have a brief interview with the dietitian to determine their usual intake. The three-day food record will include two weekdays and one weekend day, while the brief interview with the subject and dietitian will serve as an opportunity to confirm portion sizes, brand names, and other details. Both the 3-day food diary and usual intake interview will be analyzed using the Nutrition Data System (NDS) for Research (version 4.02) (University of Minnesota). Macronutrient composition of diet, as well as types of fatty acids and carbohydrates will be included in the analysis.

Stool Specimen: The subject (or subject's parent/guardian) will be provided with a kit to collect stool. If the subject cannot provide the sample at the given time, they can complete it at home. Once collected, the container will remain at 4°C and be brought back to researchers within 12 hours. The bacterial DNA will be extracted and the bacterial gene coding for the 16S RNA subunit will be characterized by Next Generation sequencing to assess the bacterial diversity.

Intervention

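### The plan does not mask the liver-fat reader to visit, so in this single-arm before-after trial a visit-related reading shift would count as a CPAP effect

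*Combined protocol and SAP*

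**What the plan says.** The primary hypothesis in Section V, item 17 (Power and Sample Size) is directional: "CPAP will decrease the intra hepatic fat accumulation measured with MRI between baseline after 4, 8 and 12 weeks of intervention in obese youth". There is one group. Section V, item 3 says that eligible subjects "will receive the CPAP and after 4, 8 and 12 weeks intervention they will undergo additional MRIs", and Statistical Methods says that the difference from baseline at each visit "will be tested using one-sample Wilcoxon signed rank-test".

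The Abdominal MRI paragraph describes two ways to obtain hepatic fat fraction:

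- A modified Dixon scan of one section through the liver, followed by the only reading rule given: "The signal from an appropriate area of hepatic tissue will be used to calculate the fat fraction".
- A three-point Dixon method covering typically 10 to 14 slices. The area wording is not repeated for this value, although it is repeated for hepatic iron.

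The document does not say which value is the endpoint, who places the area, where or how large it is, or whether placement is matched across visits. It does not mention masking of the image reader. The one image review it describes is a radiologist's check for abnormalities (Section IX).

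Baseline liver fat, judged against 5.5%, decides entry (Section V, items 3, 7 and 8). No second read of that scan is planned.

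**The concern.** Choosing an appropriate area is a judgement. The baseline judgement is made when the reader necessarily knows that the scan is a pre-treatment one, because the result determines enrolment. As the plan stands, that same reading becomes the before value in every paired difference. For the later scans the plan includes no step that would keep the visit from the reader.

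In a randomised trial a reading habit tied to visit would tend to affect both arms and drop out of the comparison. Here it goes straight into the estimated change. A slight tendency to place the area differently after treatment would be read as a fall in liver fat on CPAP. The confidence interval gives no warning, because a constant shift moves the estimate and leaves the width unchanged.

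The timing aim is exposed as well: "We will repeat the MRI multiple times to assess the shortest timeframe to significantly reduce intra-hepatic fat content". That sentence says nothing about how scans are read. But a shift between the baseline reading and all later readings would already be present at week 4, so it could make the shortest time to a reduction look shorter than it is.

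**Working it through.** **Inputs from the document (Section V, item 17).** n = 15; SD of paired differences = 1, used as a scaling unit; stated half-width 0.55; one-sample Wilcoxon signed-rank test at each visit. On the significance level: "For all analyses, a two-sided p-value of 5% will be used to test for statistical significance".

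**Input not in the document.** The size of any reading shift. It is assumed here to be constant across participants and is varied from 0 to 0.3 SD of the paired difference, with no true change in liver fat and normal differences.

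**Step 1: reproduce the plan's own figure.** The plan states "A sample size of 15 produces a two-sided 95% confidence interval" with a margin "that is equal to 0.55 when the estimated standard deviation of the paired differences is 1".

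Half-width = t(0.975, 14) × SD / √n = 2.145 × 1 / 3.873 = 0.554, which rounds to the stated 0.55. The figure reproduces.

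**Step 2: set the test.** For n = 15 the exact signed-rank test at two-sided 5% rejects when the smaller rank sum is 25 or less. Its exact two-sided level is 0.0479, so the chance of a significant decrease with no effect and no shift is 0.0479 / 2 = 0.024.

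**Step 3: impose the shift.** 200,000 simulated trials per value:

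| Assumed shift (SD of paired difference) | Significant decrease at one visit | Significant in either direction | Two-sided t-test check (noncentral t) |
|---|---|---|---|
| 0 | 2.4% | 4.7% | 5.0% |
| 0.1 | 5.2% | 6.1% | 6.5% |
| 0.2 | 10.2% | 10.5% | 11.2% |
| 0.3 | 18.0% | 18.1% | 19.2% |

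The t-test column should be compared with the either-direction column; the two follow the same pattern.

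**Step 4: three visits.** The plan tests weeks 4, 8 and 12. Suppose a significant decrease at any one of them is counted, the same shift applies at all three, and changes at different visits correlate 0.5 (a further assumption). The chance is then 6.2% with no shift, 12.4% at 0.1 SD, 22.8% at 0.2 SD and 36.4% at 0.3 SD. With correlation 0.7 the figures are 5.6%, 11.2%, 20.1% and 32.5%.

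**Step 5: compare with the planned precision.** A shift of 0.2 SD is 0.2 / 0.554 = 36% of the half-width, and 0.3 SD is 0.3 / 0.554 = 54%. Shifts that are modest against the interval still change the error rate by a factor of about four (10.2 / 2.4) to seven and a half (18.0 / 2.4).

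**The case against.** The strongest reply is that the document is silent on reading conduct and that silence is not evidence of bias. This stands for the follow-up scans. A reader might infer that whoever reads weeks 4, 8 and 12 can see the visit, or reads each scan as it arrives. The document says neither. Section VIII has study personnel recording results as they accrue, which fits sequential reading but does not establish it. What can be said is that no masking is specified. The baseline scan is different: its use for eligibility forces a read at a known visit.

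The second reply is that the endpoint may not depend on the chosen area at all. The area sentence follows the single-section method, and the three-point value could be the one analysed. This also stands. If that value is primary, the document does not show how much reader discretion is left. The answer is to name the primary value, since the plan leaves both open.

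The third reply is that the shifts are invented. They are assumed, and because SD = 1 is only a unit they cannot be turned into percentage points of liver fat. Real placement differences could also vary in sign and size between participants, which would add noise rather than a constant shift. The table shows how sensitive the test is to a shift; it does not show that one is likely.

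**Conclusion.** The point holds as a missing safeguard on the primary endpoint. The plan has a directional hypothesis, no control arm, an undefined reading area for one of its two fat measures, a baseline value read at a known visit, and no masked re-read. If a constant visit-related shift of 0.1 to 0.3 SD existed, the chance of a false significant decrease at one visit would go from 2.4% to between about 5% and 18%. This rests on n = 15, normal differences, no true change and an assumed shift.

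A reader might infer that the trial's false-positive rate is expected to be 10% or 18%, or that biased reading has been shown. Neither follows, because the document contains no reader-variability figures. Nor would masking make the before-after comparison secure. Selection on the baseline scan at 5.5% allows regression to the mean, a repeat scan may be requested for a sub-optimal image with no stated criterion, and there is still no control arm. Masked reading deals only with bias that comes from knowing the visit.

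**What to change.** Amend the Abdominal MRI paragraph and Statistical Methods as follows:

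- Keep the screening read for eligibility only.
- For the analysis, have the existing reader re-read all baseline, week 4, week 8 and week 12 scans, pooled across participants, in random order, with subject identity, dates and visit labels removed. Pooling matters: shuffling only one child's four scans for a reader who has already seen the baseline would mask weakly.
- Set in advance one region-placement rule (location, size and number of regions) and apply it to every scan.
- Name in advance which Dixon value is the primary endpoint.
- Use the masked reads in the signed-rank tests.

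The sample size of 15 and the half-width of 0.55 do not change, and no extra scan, visit or reader is needed. The cost is 15 repeat baseline reads, the work of removing labels and shuffling, and holding about 15 × 4 = 60 endpoint reads until they can be mixed. The document gives no cost figures, so the expense cannot be stated more exactly. The radiologist's check for abnormalities can go ahead at each visit as planned.

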
Despite those evidences and the importance of non-alcoholic fatty liver disease (NAFLD) in the development of metabolic diseases, the information concerning the association between fatty liver and OSA in obese children and adolescents is quite sparse and in particular is unclear whether OSA itself can cause NAFLD or the two conditions just coexist as obesity complications. In this study we will test the hypothesis that **OSA is one of the determinants of hepatic fat accumulation.** To prove our hypothesis we will select a group of individuals with NAFLD and OSA, who will undergo a weight

maintenance diet and Continuous Positive Airway Pressure (CPAP) for 12 weeks. CPAP is FDA approved and represents the leading therapy for obstructive sleep apnea in children over age 7 and 40 lbs. To evaluate the effect of the CPAP on the intra hepatic fat accumulation we will evaluate hepatic fat content with MRI at baseline and after the intervention. The choice of the MRI to assess hepatic fat content is based on the evidence that this technique has been shown to be strongly related to the liver biopsy, which represents the gold standard for the assessment of fatty liver disease (16).

References:

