Oral Glucose Tolerance Test (OGTT) is completed at baseline and at the completion of 12 weeks of c-pap intervention. The study nurse will do a nursing assessment, including measuring the patient's height, weight, waist circumference, hip circumference, blood pressure, and pulse, along with evaluation of acanthosis nigricans and striae rubrae. The subject's percent body fat, fat mass and lean mass will also be measured using a Tanita scale. The nurse will obtain a family and medical history from the patient and/or the patient's parent/guardian. In addition, before starting the OGTT, the nurse will request a urine sample from the patient for analysis of microalbumin and creatinine, and to test for pregnancy. As these subjects will be followed by Yale's Obesity clinic and/or Respiratory, if the subject's doctor orders clinical laboratory tests, we will draw these while the subject's I.V. is in place. However, the subject's insurance company will be billed for these baseline tests.

The patient will receive 1.75 g/kg to a maximum of 75g of a sugar drink, orally. The patient will have one intravenous line. "Emla" or a local anesthetic (0.1cc buffered lidocaine) will be applied before the placement of the IV catheter. Blood will be drawn 10 times over three hours. Should abnormal glucose results be found, appropriate referrals will be made. We will draw approximately 60 cc of blood during this study. The blood will be analyzed for metabolic parameters, including glucose, lactate, insulin, proinsulin, c-peptide, IL-6, TNF- α , GLP-1, free fatty acids (FFAs), leptin, and adiponectin.

As part of the protocol, blood sample will be obtained for DNA extraction. A blood sample (16mL in two tubes) will be drawn at the baseline OGTT only. The DNA extraction will be stored frozen in laboratories that are locked when not in use and the information obtained will be kept on password-protected computers.

DNA will be extracted from whole blood with the use of a Flexigene Kit (Qiagen) and stored for future analyses. (See "Genetic Testing" section for further information)

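### The primary liver-fat hypothesis is tested at weeks 4, 8 and 12 with no stated success rule; error is inflated only if any visit, or the earliest significant one, may be claimed

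*Combined protocol and SAP*

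**What the plan says.** - **Hypothesis** (Section V, item 17, Power and Sample Size). The primary hypothesis reads: "CPAP will decrease the intra hepatic fat accumulation measured with MRI between baseline after 4, 8 and 12 weeks of intervention". The three visits are listed together and none is singled out.
- **Sample size** (same place). Fifteen participants are justified by precision alone, taking 1 as the SD of the paired differences. The precision of the 95% interval is given as follows: "distance from the mean paired difference to the limits (i.e., precision or margin of error) that is equal to 0.55".
- **Tests** (item 17, Statistical Methods). "For all analyses, a two-sided p-value of 5% will be used to test for statistical significance", and "The difference in hepatic fat content between baseline and 4, 8 and 12 weeks will be tested using one-sample Wilcoxon signed rank-test". A remark about hypothesis generation for a larger study comes later, directly after the subgroup comparisons.
- **Purpose of the repeated scans** (item 3, Research Plan: General Description). "We will repeat the MRI multiple times to assess the shortest timeframe to significantly reduce intra-hepatic fat content".
- **End of intervention.** The Background says participants follow a weight "maintenance diet and Continuous Positive Airway Pressure (CPAP) for 12 weeks", and that "we will evaluate hepatic fat content with MRI at baseline and after the intervention". The glucose tolerance test is repeated "at the completion of 12 weeks of c-pap intervention".

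None of these places names a primary visit, says how many visits must be significant, orders the tests or adjusts for having three. Item 3 refers to a study design that is not reproduced in the text provided, so this statement covers the text only.

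**The concern.** One directional hypothesis goes through three tests that share a baseline, and the plan does not say what counts as success. The text allows three readings:

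- **All visits**, from the way the hypothesis is worded.
- **Week 12 only**, from the Background's comparison of baseline with after the intervention.
- **Any visit**, or the earliest significant one, as the purpose given for the repeated scans suggests.

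The same data can succeed under one reading and fail under another, and nothing prevents the choice being made once results are known. A claim that liver fat had fallen by week 4 is the kind of result item 3 looks for. It would rest on an unprotected p-value.

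**Working it through.** **1. The plan's own figure.** Half-width = t(0.975, 14 df)/√15 = 2.145/3.873 = 0.554, which rounds to the stated 0.55. It is reproduced and not in dispute. It is an interval half-width, not an assumed effect.

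**2. One test.** With n = 15, the exact signed-rank test at two-sided 5% rejects when the smaller rank sum is 25 or less. P(W ≤ 25) = 0.02396 in each direction, so the two-sided size is 2 × 0.02396 = 0.0479. A cut-off of 26 would give 0.0554, which is too large. A false decrease therefore has probability 2.4%.

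**3. Three tests, if independent.**
- Any false decrease: 1 − (1 − 0.02396)³ = 0.0702.
- Any false finding in either direction: 1 − (1 − 0.04791)³ = 0.1370.
- All three false decreases: 0.02396³ = 0.000014, or about 0.001%.

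**4. Three tests, correlated.** The documents do not give the correlation between the change scores, so it is an assumption. If raw values have equal variance σ² and equal correlation ρ, each change has variance 2σ²(1 − ρ) and two changes have covariance σ²(1 − ρ). Their correlation is then 0.5 because of the shared baseline. I take 0.5-0.7 as the main case and 0-0.9 as the range. Simulating the exact test with n = 15, normal changes and no true effect gives:

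| Correlation of changes | Any visit: false decrease | Any visit: either direction | All three: false decrease |
|---|---|---|---|
| 0 | 7.0% | 13.7% | 0.001% |
| 0.5 | 6.2% | 12.4% | 0.1% |
| 0.7 | 5.5% | 11.0% | 0.3% |
| 0.9 | 4.3% | 8.6% | 0.9% |

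The comparators for one test are 2.4% (decrease) and 4.8% (either direction). Autoregressive raw values with correlation 0.3 to 0.9 give 6.0% to 5.5% for any false decrease. Heavy-tailed data (t, 3 df) with a shared baseline give 6.2%.

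**5. False early claims.** Suppose there is no effect at weeks 4 and 8 and an effect of 0.55 SD at week 12 (assumed). A false decrease at week 4 or 8 is then found in 4.4% to 4.1% of trials at correlations 0.5 to 0.7 (4.8% to 3.5% over 0 to 0.9). Testing in the order week 12, week 8, week 4, and stopping at the first visit without a significant decrease, gives 2.1% to 2.3% (1.2% to 2.4% over 0 to 0.9).

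**The case against.** **The stated hypothesis is conjunctive.** The one sentence that sets out the primary aim joins the three visits with *and*. Read that way, the error rate is far below the single-test rate. This stands: the defect is a rule left unstated, and inflation follows from only one of the readings. A reader might infer that the trial runs a 5.5-6.2% chance of a false decrease, or about 14% in either direction. The documents do not support that. They nowhere state an any-visit rule; it is an inference from the purpose given for the repeated scans. They also give no correlation from which one figure could be fixed.

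**Week 12 is obviously primary.** It is the end of the intervention, but no section calls it primary. The Background phrase is a summary and is compatible with scans at all three visits.

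**The work is labelled hypothesis-generating.** That remark follows the subgroup comparisons and most naturally refers to them.

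**The study is small and sized on precision.** True, and this limits the weight of the point. It does not supply the missing rule for tests that the plan does specify at 5%.

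**The rates may not be this trial's actual error rates.** This also stands. They need changes symmetric about zero. Participants are selected on a screening MRI, and no separate baseline scan is described. The $340 maximum payment equals 2 × $50 (glucose tolerance tests) + 4 × $60 (MRIs), which fits the selecting scan also being the baseline. Regression to the mean could then add false decreases at every visit, under one test or three.

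**Conclusion.** The point holds as an unspecified decision rule for the primary hypothesis. The all-visits and week-12-only readings do not inflate error. If any visit suffices, or the earliest significant visit is claimed, the chance of a false decrease is roughly 1.8 to 2.9 times that of one test (4.3/2.4 to 7.0/2.4). The narrower 5.5-6.2% depends on the assumed correlation of 0.5-0.7. All these rates assume no true change and symmetric changes. The matter is modest but worth settling, because the shortest-timeframe conclusion is an intended output and has no error-controlled procedure behind it.

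**What to change.** Add to Statistical Methods, before the data are analysed:

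> The primary test is the change in hepatic fat from baseline to week 12 (signed-rank, two-sided 5%). If week 12 shows a significant decrease, week 8 is tested at two-sided 5%; if week 8 also shows one, week 4 is tested at two-sided 5%. The shortest timeframe is the earliest visit with a significant decrease in this sequence. Visits not reached are descriptive. The mean paired change with its 95% CI is reported at every visit.

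The last sentence reports the quantity on which the sample size was justified. If the sponsor gives the early visits equal weight, Holm across the three visits, or an explicit all-visits rule, is an acceptable alternative.

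No extra participants or scans are needed. Under the sequence the week-12 test is unchanged and, with symmetric changes, a false decrease stays at 2.4% at any correlation. The price is harder early claims. The documents give no effect size, so the power figures below are illustrative, at correlations 0.5 to 0.7:

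| Assumed effect at weeks 4/8/12 (SD) | Claim | Unadjusted | Sequence | Holm |
|---|---|---|---|---|
| 0.55/0.55/0.55 | Week 4 | 49% | 22-28% | 35% |
| 0.55/0.55/0.55 | Week 12 | 49% | 49% | 35% |
| 0.3/0.55/0.8 | Week 4 | 18% | 13-16% | 14-15% |
| 0.3/0.55/0.8 | Week 12 | 80% | 80% | 63% |

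Under the sequence, week 4 is claimable only if all three visits show a significant decrease. The week-4 sequence figures are therefore also the success rates of an all-visits rule.
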